### Study Design:

A prospective pretest and posttest intervention study will be conducted at the post-Covid clinics in Riyadh, Saudi Arabia.

### Study Setting and duration of study:

The study will be conducted at the post-COVID clinics in Riyadh region.

The duration will be for 4-week, 3 sessions per week. Each session will last for 45 minutes.

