## **Intervention**

The intervention will be based on a rehabilitation program approved by the MOH. (24) The rehabilitation sessions will include breathing techniques, aerobic exercises, strength training, and education. As part of the regular rehabilitation protocol, each participant will undergo the following rehabilitation program with a specialized licensed clinician.

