### **1. Respiratory Exercises**

- Active cycle of breathing technique (ACBT)

The participants will start with exercises 1-3 at least twice a day and increase the frequency to four to six times a day. The exercises will include three stages: breathing control, chest expansion, and exhalation. Breathing control will be achieved by asking the participants to breathe in and out gently through the nose if possible. If the breath is exhaled through the mouth, the participant will be instructed to purse their lips as if they were blowing out a candle. The participant will be asked to try to gradually make their breathing slower. Following that, the participant will be instructed to take a long, slow, deep breath in through their nose if they can while keeping their chest and shoulders relaxed, then breathe out gently without forcing the air out and relax, as if sighing. Finally, they will be asked to “huff”, which is exhaling through an open mouth and throat instead of coughing. This helps move sputum up the participant’s airways so that they can be cleared in a controlled way. To “huff,” they must quickly squeeze air from their lungs and let it out through their open mouth and throat, as if they were trying to mist up a mirror or their glasses. They will be asked to use their abdominal muscles to help them squeeze the air out, but not to force it so much that they cause wheezing or tightness in their chest. If huffing clears their sputum, then they should not need to cough. They should only cough if the sputum can be cleared easily. They should continue the breathing exercises for about 10 minutes, ideally until their chest feels clear of sputum.

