### **2. Aerobic exercises**

The aerobic exercises will include walking up and down stairs, walking at home, cycling, and dancing. Each session should last for 30–60 minutes per day and start with low-intensity exercise. The intensity will be increased by 10% every week. A limit of 70% of the maximum heart rate will be set. (25)

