### **3. Progressive strengthening training**

Strengthening exercises are designed to improve muscle strength and endurance. The frequency and intensity will be adjusted for each participant individually. The participants will be requested to perform the following strengthening exercises. Standing heel raise: the participant should hold on to a chair, reach overhead while standing on their toes and bring their hands together. This should initially be repeated two to three times, increasing gradually to eight times (for one set). Mini squats should be performed while holding onto a chair and breathing. Wall push-ups should be held for eight seconds. Core exercises should start with 10–15 repetitions and then repetitions should slowly be increased. Participants should perform sit to stand

exercises for one minute. All these exercises should initially be repeated two to three times per day and frequency should be increased gradually to 10 times a day.

4. Mobility training or gait training to increase endurance.

Every day, participants will be asked to walk for at least 30 minutes without stopping as part of a mobility training program to improve endurance. Participants will also begin walking on flat surfaces before progressing to uneven surfaces. As the participants' mobility progresses and they gain endurance, they will be asked to challenge themselves by walking on hills and inclines for 10 minutes, increasing the frequency of this exercise to three times a day. They will be asked to walk five times per week, ascending and descending stairs with assistance if needed.

5. Home-exercise program (HEP)

All the activities, including a walking program, resistance exercises, and breathing techniques, should be continued at home.

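### Do the stated exercise times contradict the 45-minute session, and does the unstated split between clinic and home require a change to the plan?

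*Combined protocol and SAP*

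**What the plan says.** The Study Setting and duration section gives the contact schedule: "The duration will be for 4-week, 3 sessions per week. Each session will last for 45 minutes".

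The Intervention section lists what the sessions contain: "The rehabilitation sessions will include breathing techniques, aerobic exercises, strength training, and education". It adds that "each participant will undergo the following rehabilitation program with a specialized licensed clinician". It bases the programme on one approved by the health ministry, which it cites but does not reproduce.

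The subsections then give amounts:

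- **Respiratory exercises:** "The participants will start with exercises 1-3 at least twice a day and increase the frequency to four to six times a day", and "They should continue the breathing exercises for about 10 minutes, ideally until their chest feels clear of sputum".
- **Aerobic exercises:** "The aerobic exercises will include walking up and down stairs, walking at home, cycling, and dancing", and "Each session should last for 30–60 minutes per day and start with low-intensity exercise".
- **Strengthening:** "All these exercises should initially be repeated two to three times per day and frequency should be increased gradually to 10 times a day". Apart from one minute of sit-to-stand, no total time is given.
- **Mobility training:** a daily walk of at least 30 minutes, and a later sentence asking for walking five times a week that goes on to mention stairs.
- **Home programme:** all activities are to be carried on at home, with no amount stated.

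The Procedures section has an investigator supervise the therapists closely. The questionnaires and physical tests are outcome and baseline measures only. The Statistical analysis section compares matched scores before and after the programme and uses no attendance or adherence variable.

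**The concern.** Read straight through, the Intervention section seems to put four components, with a clinician, into a 45-minute visit, and two of those components can take up to 70 minutes. That looks like a plan that cannot be delivered as written.

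The alternative reading, in which much of the exercise is done at home, raises a different worry. Twelve visits of 45 minutes would then not be the whole exposure. The plan does not say how much of each component is supervised, and no record of visits attended or home exercise done is described. In a single-group study the description of the programme carries much of the report's value. What is not recorded during the four weeks cannot be reliably recovered afterwards. At stake would be whether a reader could say what was prescribed and done, and could repeat it.

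**Working it through.** **Inputs.** Session 45 minutes, 3 per week, 4 weeks (Study Setting). Breathing about 10 minutes, at least twice daily and rising to four to six times (Respiratory Exercises). Aerobic 30 to 60 minutes per day (Aerobic exercises). Daily walk of at least 30 minutes (Mobility training). Education and most strength work have no stated time.

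**Clinic contact.** 4 × 3 = 12 sessions; 12 × 45 = 540 minutes in total; 3 × 45 = 135 minutes a week.

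**Reading A: the full daily amounts fall inside the visit.**

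- Shortest: 10 + 30 = 40 minutes, which leaves 5 for everything else.
- Longest: 10 + 60 = 70 minutes, which is 70 − 45 = 25 over.
- Break point: 45 − 10 = 35 minutes of aerobic work.
- Share of the aerobic range above the break point: (60 − 35)/(60 − 30) = 25/30 = 83%.

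The 83% is a share of a permitted range, not a probability. A range allows the clinician to stay at its lower end.

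**Reading B: the amounts describe the whole programme.** Three visits a week cannot contain exercises prescribed several times every day. If about 10 minutes applies to each round, breathing alone takes 2 × 10 × 7 = 140 to 6 × 10 × 7 = 420 minutes a week, against 135 clinic minutes. The Aerobic subsection counts by the day and names an activity done at home, and the home programme covers the rest. The Intervention section says that sessions include the components; it does not say that each daily amount is completed there. Reading A therefore cannot be what the frequencies mean, whereas Reading B accommodates every sentence.

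**How much falls outside the clinic under Reading B?** There are 28 − 12 = 16 days without a visit. Assume that walking and breathing on visit days are all done in session, which keeps the outside total low. Breathing at the starting frequency then adds 16 × 10 = 160 minutes if 10 minutes is the day's total, or 16 × 2 × 10 = 320 if it is per round.

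| Assumption on the 30-minute walk | Walking outside clinic | Plus breathing (160 to 320) | Clinic total |
|---|---|---|---|
| Every day | 16 × 30 = 480 | 640 to 800 | 540 |
| Five times a week | (20 − 12) × 30 = 240 | 400 to 560 | 540 |

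The second row assumes 30 minutes for the five weekly walks, because that sentence gives no duration. The plan states neither total. At the per-round ends (800 and 560), the visit-day assumption requires 30 + 2 × 10 = 50 minutes of walking and breathing in a 45-minute visit, so those figures are lower bounds that could not quite be met. Home exercise is plainly substantial, but whether it exceeds clinic time depends on the reading.

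**The two walking sentences.** The sentence with the weekly count refers to stairs. A daily walk together with stair walking on five occasions a week is coherent.

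**Effect on the analysis.** The paired t-test or Wilcoxon signed rank test uses each participant's scores before and after. Session length, home minutes and attendance do not enter it.

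**The case for a change.** The strongest case for a change is that Reading B resolves the overrun but leaves the exposure undefined. Depending on how the walking text is taken, the outside total moves by 480 − 240 = 240 minutes, so the plan does not pin down what was prescribed. Strengthening is adjusted to the individual, so exposure will also differ between participants. Supervision of therapists does not capture what happens at home, and the Sample size section itself expects 30% dropout. A schedule table and a one-page log would be cheap, and the information is lost if it is not collected at the time.

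Much of this stands as an observation. The split is not quantified in the text available, no record is described, and 12 × 45 minutes understates the programme. Whether the cited ministry programme contains a schedule cannot be seen from here.

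It does not carry through to a needed change. The amounts are whole-programme prescriptions tailored by a clinician, so a single fixed total is not implied. A log of self-reported home minutes would add description. In one group with no control, it could not by itself tell low adherence from lack of effect. The change after being offered the programme can be estimated and described without it.

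**Conclusion.** No change follows. The apparent conflict of 40 to 70 minutes against 45 exists only if the daily amounts are all to be completed in the visit. The daily frequencies, the activity placed at home and the home programme make the whole-programme reading the sensible one, and under it the sections agree.

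What is left is missing detail about the division between clinic and home and about recording. Its size can be given only conditionally: 640 to 800 minutes outside the clinic if the walk is literally daily, or 400 to 560 if it is five times a week, beside 540 clinic minutes. These figures describe prescribed exposure, not an effect on any result. The paired comparison and the conclusion it can support are the same either way.

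This rests on two assumptions: that the session list names components and not full daily doses, and that the result is reported as the change following an offer of the programme. No view is taken on any duration or frequency.

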### Study subjects/participants:

#### Inclusion Criteria:

- The participants' ages from 18-45 years old
- Participants who are referred to the post-COVID clinics.
- Participants who are discharged from the hospitals between 3 to 6 months ago.

**Exclusion Criteria:**

- If they have any viral pneumonia, acute respiratory distress syndrome (ARDS), cardiovascular instability, pulmonary embolism, and disability or disorders.
- Musculoskeletal disorders
- Neurodegenerative diseases
- Patients unable to walk.

**Recruitment:**

- Participants who are referred to the post-COVID clinics.
- Each participant who is referring to the clinic will be asked if he/she willing to be part of the study.

**Procedures:**

The research team will provide a full explanation of the study design, methods, and protocols to each participant. Informed consent then will be signed by the participants before starting the study.

The following safety precautions will be observed when assessing and training the participants. A safety belt will be placed around the participants' hips if needed. The participants will be requested to place their arms around the therapist's hips if they need to stand or walk. Therapists should avoid lifting the participants unless they ask for additional assistance. The participants should be given time to stand using their own strength. The therapists should stay close to the participants during transfer and walking, and the participants' weight should be kept close to the therapist's center of gravity to avoid falling. When the participants feel fatigued, the assessment of their training should cease immediately, and the participants should be given the opportunity to take a rest. After each assessment and training session, the participants should be given a two-to-three-minute break. Furthermore, the therapists must be closely supervised by an investigator to ensure that all research activities are carried out in accordance with the approved study protocols.

After signing the informed consent, the participants will answer this questionnaire.

**Demographic questionnaire**

After signing the informed consent form, subjects will be asked to complete a baseline demographic questionnaire that will record the following variables: age, gender, height (cm), weight (kg), educational level, job status, marital status, smoking status, and number of COVID-19 vaccine doses.

**Surveys** will be used before and after the intervention:

In addition, participants will complete the following validated questionnaires.

- The BERG Balance Scale will be used to assess participants' ability (or inability) to safely maintain their balance (static, dynamic, and fall risk) during a series of scheduled tasks. This is a 14-item objective measure list, with each item answered using a five-point ordinal scale ranging from 0 to 4, with 0 indicating the lowest level of function and 4 the highest level of function. The questionnaire takes approximately 20 minutes to complete. The participants should understand that they must maintain their balance

while attempting the tasks. The choice of which leg to stand on or how far to reach is left to the participants. Poor judgment will adversely influence their performance and scoring. A higher score indicates good functional balance.

- The Modified Medical Research Council (mMRC) Dyspnea Scale will be used to assess participants' degree of baseline functional impairment due to dyspnea from respiratory diseases. The mMRC 0–4 scale was developed by the American Thoracic Society as a modification of the dyspnea index originally proposed by the British Medical Research Council, which uses a 1–5 scale.
- The Depression, Anxiety, and Stress Scale - 21 Items (DASS-21). This is a set of three self-report scales designed to measure emotional states of depression, anxiety, and stress. Each of the three DASS-21 scales contains seven items, divided into subscales with similar content.
- The Fatigue Assessment Scale (FAS). This is a 10-item scale used to evaluate symptoms of chronic fatigue. It is quick and easy for participants to complete and is not time-consuming.
- The Quality of Life (QOL) - short form SF-36. This 36-item questionnaire uses eight subscales to measure physical functioning, physical role, bodily pain, general health, vitality, social functioning, emotional role, and mental health. An Arabic version of the QOL questionnaire will be used.

Then, these measurements will be used to measure physical status, endurance, and capacity.

- 6-min walk test (6-MWT) will be assessed using two cones will be placed at 30 meters in an unimpeded walkway. The patients are instructed to walk as far as possible for six minutes (recorded on a timer) at a comfortable speed between the cones, with every turnaround, the cones being quick pivots. The total distance walked was recorded at the end of 6 minutes.
- 10-meter walk test (10MWT) will be measured by a clear pathway of at least 10 m in length in a designated area over solid flooring is required. The pathway will be measured and marked at the start and end points of a 10-m walkway. A mark will be added at 2 m and 8 m (identifying the central 6-m, which will be timed). The patients will ask to walk comfortably until the end of the mark, then walk fast again until the of the mark. Two trials of each walk will be recorded, and the best score will be recorded.
- A Time Up and Go (TUG) test will be evaluated using a chair will be placed in a hallway, and tape will be used to mark 3-meters in front of the chair. The test starts with the patient will be sitting on a chair. Then the patient will be instructed to stand up from the chair on command, walk 3 meters, turn around, walk back to the chair, and sit down with the therapist recording the time taken from standing up from the chair to the point he sits back.
- 1-min sit-to-stand test (1-MSTST) will be assessed by asking the patients to sit comfortably in the chair with both feet flat on the ground, and a timer will be set for one minute. Then the patients will be instructed to hold the hand close together loosely and stand up from the chair until the legs are completely extended, followed by sitting back down again, which counts as one. The patients will continue standing and sitting as many times as they can in one minute. The total number of sit-to-stand will be recorded at the end of one minute.

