### **Statistical analysis**

The data will be analyzed using multivariate statistics to compare more than two variables at baseline and afterward. Continuous variables will allow a mean to be obtained with standard deviation (normal data) or a median with an interquartile range (skewed data), while categorical variables will be obtained as numbers and percentages. The score data from the 6MWT, 10MWT, TUG, and STS tests will be examined using a paired t-test or a Wilcoxon signed rank test to facilitate comparison of matched pre-test and post-test scores, in addition to observations of the behavior and differences in the survey data.

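### The TUG, 6MWT and 1-MSTST each have one scored attempt and no stated familiarisation, so in this one-group paired comparison any retest gain adds to the apparent programme effect.

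*Combined protocol and SAP*

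**What the plan says.** All references are to the combined protocol and SAP.

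- **Design.** Study Design states: "A prospective pretest and posttest intervention study will be conducted at the post-Covid clinics in Riyadh, Saudi Arabia". Under Intervention, "each participant will undergo the following rehabilitation program with a specialized licensed clinician". No comparator, repeated baseline or run-in is described.
- **Interval.** Study Setting and duration of study: "The duration will be for 4-week, 3 sessions per week".
- **TUG** (performance tests, listed after the surveys under Demographic questionnaire). One performance is timed: "Then the patient will be instructed to stand up from the chair on command, walk 3 meters, turn around, walk back to the chair". No practice run, repeat or best-of rule is given.
- **6MWT** (same list). One walk is described: "The total distance walked was recorded at the end of 6 minutes". The instruction asks for the greatest distance and also for a comfortable pace.
- **1-MSTST** (same list). One minute of repetitions is counted, and no practice is mentioned.
- **10MWT** (same list). Here the number of attempts and the scoring rule are given: "Two trials of each walk will be recorded, and the best score will be recorded".
- **Analysis.** Statistical analysis applies to all four tests a "paired t-test or a Wilcoxon signed rank test to facilitate comparison of matched pre-test and post-test scores", with no allowance for repeat testing.

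**The concern.** For three of the four performance tests, the procedure as written makes the baseline score the participant's first scored attempt and the post-test score the second. Someone who has met the chair, the turn, the cones or the one-minute count before may do better for that reason alone. Such a gain favours the programme. With one group there is nothing to subtract it against, and the paired test attributes the whole mean change to whatever happened between visits. This is systematic error, so more participants make it more likely to reach significance.

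The 1-MSTST belongs here with the TUG and the 6MWT. Sit-to-stand is also a prescribed strengthening exercise, but training comes after baseline and cannot make the baseline attempt a familiar one. The 10MWT is less exposed because the better of two trials is kept at each visit, though no unscored practice is described for it either.

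At stake is how far the change in these scores can be read as the effect of rehabilitation.

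**Working it through.** **1. What the procedures specify**

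| Test | Scored attempts | Practice attempt | Scoring rule |
|---|---|---|---|
| TUG | 1 | not stated | single time |
| 6MWT | 1 | not stated | single distance |
| 1-MSTST | 1 | not stated | single count |
| 10MWT | 2 of each walk | not stated | best |

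**2. What the paired comparison estimates**

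Mean change (signed so that positive is better) = programme effect + retest gain + natural recovery + regression to the mean + other shifts between visits.

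Nothing in the design or analysis separates these terms. If the programme effect is zero and the retest gain is not, the paired test has a non-zero mean to find.

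**3. Illustration of the consequence**

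Inputs from the documents: 60 participants and a 30% dropout rate (Sample size). The text does not make clear whether 60 is before or after dropout, so both cases are shown: 60 × (1 − 0.30) = 42 completers, or 60 completers. The stated 60 cannot be reproduced, because neither the population size nor the percentage used is given. This point does not depend on it.

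Inputs assumed, because the documents give none: two-sided 5% test; no programme effect and no other shift between visits; retest gain d, in SDs of the paired difference, from 0.1 to 0.4. A value of 0.05 is added to show a near-negligible gain.

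Formula: the paired t statistic follows a noncentral t distribution with n − 1 degrees of freedom and noncentrality d√n. The probability of a significant improvement is P(T > t₀.₉₇₅,ₙ₋₁). The critical values are 2.020 for n = 42 and 2.001 for n = 60.

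| d | d√42 | P, n = 42 | d√60 | P, n = 60 |
|---|---|---|---|---|
| 0 | 0 | 2.5% | 0 | 2.5% |
| 0.05 | 0.324 | 5.0% | 0.387 | 5.7% |
| 0.1 | 0.648 | 9.2% | 0.775 | 11.5% |
| 0.2 | 1.296 | 24.4% | 1.549 | 33.1% |
| 0.3 | 1.944 | 47.6% | 2.324 | 62.8% |
| 0.4 | 2.592 | 71.6% | 3.098 | 86.2% |

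These count the improvement tail only. Adding the opposite tail changes little: at n = 42 and d = 0.1 the total is 9.7%.

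For any fixed d above zero the probability rises with n, as expected of a bias. No after-fix figure is computed, because the documents do not allow an estimate of how much gain a practice attempt would remove.

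**The case against.** **Silence is not exclusion.** The protocol does not say that practice is withheld, and the two-trial rule for the 10MWT concerns scored trials. This stands, so the claim is limited to what the text provides for. But if practice is left to each therapist, it may be given to some participants or at one visit only, which is also undesirable in a paired comparison. Either way the procedure needs a sentence.

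**The size is wholly assumed.** This also stands. The documents give no retest gain, no SD for these tests, and nothing on whether a first-attempt gain lasts through a four-week programme. The percentages follow from the chosen d and show how sensitive a one-group paired test is to any shift. They do not show that the shift is large here; at 0.05 SD the rate is only about 5% to 6%.

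**The larger problem is the missing comparator.** Participants are three to six months past discharge, so natural recovery acts on the same difference, as may regression to the mean. Familiarisation addresses neither. This stands, but a comparator would mean a different study, whereas retest gain can be reduced within this one.

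**Practice has its own cost.** Under Procedures, assessment stops when a participant is fatigued. Extra exertion before the scored test might tire weaker participants more at baseline than later, and so bias the change in the same direction. For the 6MWT, a short circuit teaches the turns but not how to pace six minutes. Both points stand and limit what should be asked for on that test.

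**Stronger readings to avoid.** A reader might infer that the plan rules out practice, that the observed gains would be mostly artefact, or that one practice run would make the change attributable to the programme. The documents support none of these: they are silent on practice, they give no size for the gain, and the other uncontrolled changes would remain.

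**Conclusion.** The point holds in a limited form. Followed as written, the plan scores a single attempt of the TUG, the 6MWT and the 1-MSTST with no provision for familiarisation, in one treated group, and tests plain paired differences. Any retest gain is then counted with the programme effect in three of the four performance tests, and less so in the 10MWT. The direction follows from the design; the size is unknown.

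The tabulated rates are illustrative only and rest on the assumed gain, a two-sided 5% test and no other change between visits. No primary outcome is named, so the effect on the study's main conclusion cannot be judged. The change is worth making because it is inexpensive, not because a large bias has been shown.

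**What to change.** In the performance-test procedures:

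- **TUG:** add one unscored practice run immediately before the scored run, at both visits.
- **1-MSTST:** add a brief unscored demonstration and practice of the movement before the timed minute, at both visits.
- **6MWT:** use identical standardised instructions at both visits, including a single wording on pace. Allow at most a short familiarisation with the turns, followed by the break already provided under Procedures. State that this does not remove gain from learning to pace the walk.
- **All three:** keep instructions, number of attempts, rest and scoring rule the same at both visits, and write them down.

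In Statistical analysis, state that results will be reported as pre-post change that may include retest gain, natural recovery and regression to the mean.

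The cost is a few minutes more per visit with the same staff and equipment, some added exertion before the scored test, and probably a smaller observed change. The bias is reduced by an unknown amount and not eliminated, since the post-test remains a later exposure than the baseline.
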